Randomized clinical trial with passive control, triple blind (for the patient, the physiotherapist applying the technique and evaluator), with a parallel and multicenter design. The study will have two arms, the intervention group will undergo neuromodulation treatment with the NESA XSIGNAL® device and the control group will not carry out any intervention, but both will be evaluated for the same variables at the same times.

SCOPE AND STUDY POPULATION:

Multicenter study whose collaborating entities correspond to the University of Las Palmas de Gran Canaria, Alfonso X el Sabio University, the Pontifical University of Salamanca and the University of Alcalá de Henares. The study population will be students from the collaborating universities, corresponding to first-year health sciences degrees. For the selection of the sample, a non-probabilistic convenience sampling will be carried out, which allows selecting those accessible cases that agree to be included.

CALCULATION OF THE SAMPLE:

The present study is proposed as a pilot study due to the absence of similar studies in this field that allow a

calculation of the adjusted sample size. For this, 80 participants will be included, who must meet the established selection criteria.

CRITERIA FOR SELECTING THE PARTICIPANTS

INCLUSION CRITERIA.

- Healthy people
- Be enrolled in a degree in health sciences at the partner universities in the study in the first year.
- Optimal cognitive abilities and mentally competent to participate in the study.
- In cognitive conditions to complete the study questionnaires
- Have an optimal command of the Spanish language to complete the questionnaires.
- Signing of the informed consent for participation

EXCLUSION CRITERIA.

- Present some of the contraindications for a treatment with NESA X SIGNAL®: Pacemaker or other electrical surgical device, internal bleeding, do not apply electrodes on skin in poor condition, with ulcerations or wounds, acute febrile processes, pregnancy, acute thrombophlebitis and / or phobia of electricity, and pregnant.
- Combine another pharmacological treatment that influences the variables to be evaluated during the study.

ELIMINATION CRITERIA.

- Missing an intervention session of the 10 scheduled sessions.

RECRUITMENT OF PARTICIPANTS AND EVALUATION PROCESS.

Phase 1. Dissemination of the study

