The dissemination of the participation of the subjects in the study will consist of making an initial contact through the teachers responsible for each center. Once informed, the students will receive an email with the complete information sheet containing the description of the study, the objective, the justification, the risks and benefits derived from participation, everything related to the protection of their personal data and the way of contacting the researcher in charge of each center (ANNEX 01). In the same actions, the established selection criteria will be reported.

Phase 2. Call for anamnesis of those interested in participating in the study and selection of study subjects.

Phase 3. Acceptance of participation in the study by signing the informed consent (ANNEX 02)

Once the consent is signed, the participant will fill in the participant's demographic characteristics questionnaire (ANNEX 03) and measures of baseline variables.

Next, the participant will be summoned to the laboratory of the corresponding university for the application of the evaluation intervention within the corresponding deadlines and indicated in the information sheet of the study.

RANDOM ASSIGNMENT:

Patients who agree to participate will be randomly assigned to one of the 2 arms of the study (real device or control), using a fixed-size block design generated by the data manager to guarantee balanced randomization for each of the arms and in each of the participating universities. The assignment process will be carried out hidden and will be carried out by the support researcher in the Unit indicated for this study. Each research subject will be assigned an identification code corresponding to correlative numbers from 1 to 80, with 1-20 subjects from the UPSA, from 21-40 students from the Alfonso X el Sabio University, from 41 to 60 students from the University of Las Palmas and from 61 to 80 from the University of Alcalá.

BLINDING:

The intervention to which the subjects have been assigned, the specialist and the researcher who collects the information and performs the follow-ups will be blinded. Data analysis will also be performed in a blinded fashion.

INTERVENTION PROTOCOLS

For neuromodulation:

Group 1: Application of Nesa microcurrents through the NXSIGNAL® generator twice a week.

The volunteer subjects of the study are treated with the NXSIGNAL® device in sessions of 60 minutes, twice a week and for 5 weeks (10 sessions).

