Since it is estimated that the total sample will be registered during the first month, a quality audit will be carried out on a weekly basis. In them, the following will be carried out:

- Ascending ordering of the data: revision of the variable date of inclusion and time of exposure.
- Exploration of the variable.
- List of Frequencies for the variables: age, sex, marital status, use of drugs and perception of health.

According to this procedure, we could detect inconsistencies in the data dump, as well as identify the person who executed it, guided by the code assigned to the registrar already mentioned in the first section. In addition, the code could be associated with the name of the document when it is edited and saved, so that it would be known who last entered or evaluated the document. In both situations, in the event of detecting an error, the person in charge would be notified immediately to correct it.

3.- Audit mechanism: Cross Audit

Each logger, weekly the first month, and biweekly the following months, will review the data dumped from another logger in the team from the last review to date, according to a random sequence established by the principal investigator. The scheme to follow would be the following:

4- Ethical and legal considerations. Procedures to keep information and comply with legal considerations regarding data protection.

All data will be collected by computer in an encrypted Excel document (Microsoft Office Excel 2019 MSO 64-bit program). They will be downloaded in electronic format from the Google Forms platform, and a database will be created whose access will be encrypted, which will make it only accessible through a key known

exclusively to the researchers responsible for each project center.

The pseudonymization used in completing the questionnaires will make the personal data collected in no case identifying a natural person.

The estimated time for the coding and analysis of the results is estimated at 2 months, after which time the database will be erased, keeping only the statistical data. The destruction will be done by means of computer erasure by means of a program that allows deleting specific folders, eliminating hard drives and filling in empty spaces on the disk, so that the elimination technique is safe and the deleted information is not allowed to be recovered again. Statistical data will be kept for the time necessary for the adequate dissemination of the results.

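### Fixed-size blocks within 20-student universities, an unmasked control and no stated timing or release of assignment: the protocol does not show that allocation is unpredictable

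*Combined protocol and SAP*

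**What the plan says.** RANDOM ASSIGNMENT sets out two arms, allocated "using a fixed-size block design generated by the data manager to guarantee balanced randomization". That balance is meant to hold by arm and within every university. Identification codes are "correlative numbers from 1 to 80, with 1-20 subjects from the UPSA", and the other three universities receive 20 codes each. CALCULATION OF THE SAMPLE agrees on the total: "80 participants will be included, who must meet the established selection criteria". The section also says that the assignment is concealed and carried out by a support researcher. It gives no block size, no concealment mechanism, no statement of who learns each result and when, and no statement of whether students are randomised singly or as a group.

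DESIGN says that "the control group will not carry out any intervention", and the Group 2 paragraph under INTERVENTION PROTOCOLS confirms that no device is applied. Group 1 attends ten 60-minute device sessions over five weeks.

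On entry to the trial, SCOPE AND STUDY POPULATION states that "a non-probabilistic convenience sampling will be carried out, which allows selecting those accessible cases that agree to be included". RECRUITMENT OF PARTICIPANTS places an anamnesis and the selection of subjects (Phase 2) before consent and baseline measures (Phase 3). On timing, the quality-audit section says: "Since it is estimated that the total sample will be registered during the first month".

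**The concern.** Concealing a randomisation list stops staff from reading it. It does not stop them from reasoning forward from allocations already made, if they can see those. Blocks of one size, forced to balance within a small centre, make such reasoning productive: each allocation to one arm raises the chance that the next goes to the other, and near the end of a block the result is fixed.

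The other ingredient is discretion over who enters next. Here students are chosen by convenience and after an anamnesis, and the eligibility criteria set no range for baseline sleep or stress. A recruiter who expects a particular arm could, knowingly or not, bring forward or hold back a student who seems keen, stressed or a poor sleeper. The groups would then differ before treatment. The planned between-group comparison is an independent-samples t test without baseline adjustment, so such a difference would pass straight into the sleep, stress and grade results. Adjustment could remove only the part captured by measured baselines.

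**Working it through.** **Inputs from the protocol.** Two arms; balance by arm within university; 20 students in each of four universities, and 4 × 20 = 80 agrees with the stated total. A 1:1 ratio is inferred from the word balanced, since the ratio is not written out. Block size is not given.

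**Assumptions for every figure below.** Students are randomised one by one, and those selecting students see earlier allocations at their university.

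**Possible block sizes.** Equal blocks that guarantee 10:10 in 20 students must be even and divide 20, so the size b is 2, 4, 10 or 20. Write b = 2m.

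**Allocations known with certainty (block size known or inferred).** Once one arm has filled its m places, the rest of the block is determined. The expected number of such places is 2m/(m + 1), a share of 1/(m + 1).

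**Best guess.** The recruiter always guesses the arm with fewer allocations so far and scores one half at a tie. Expected correct guesses per block are m + ½[2^(2m)/C(2m, m) − 1]. For b = 4 this is 2 + ½(16/6 − 1) = 2.833, and 2.833/4 = 0.708. The strategy needs only the running imbalance, not the block size.

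| Block size | Share certain | Per university | Of 80 | Best guess correct |
|---|---|---|---|---|
| 2 | 1/2 = 50% | 10.0 | 40.0 | 75% |
| 4 | 1/3 = 33% | 6.7 | 26.7 | 71% |
| 10 | 1/6 = 17% | 3.3 | 13.3 | 65% |
| 20 | 1/11 = 9% | 1.8 | 7.3 | 62% |

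The benchmark for an unpredictable sequence is 0% certain and 50% guessed. If the block size stays unknown, the 50% to 9% column does not apply as it stands. Anyone who knows the 10:10 target can still determine at least the last allocation at each university.

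**What this could do to the t test (illustration only).** Trials with no true effect were simulated: four centres of 20, two-sided test at 0.05, 3,000 trials per setting. The recruiter was assumed to bring in students whose outcome is shifted 0.25 SD in the direction of the guessed arm. The false-positive rate was about 18% to 20%, 14%, 10% and 8% for blocks of 2, 4, 10 and 20, in place of 5%. The range for blocks of 2 is two runs of what is there the same strategy, and shows the simulation error. The 0.25 SD is not a figure from the documents.

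**Would varying the block size help?** Under the same running-imbalance guess, sizes drawn at random from 4, 6 and 8 give 67% correct, and from 2, 4 and 6 give 70%. That is slightly below a fixed block of 4 (71%) but above a fixed block of 10 (65%) or 20 (62%). Varying sizes reduce certain knowledge but do little about guessing.

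**One-step allocation.** If all 20 students of a university are allocated together, no earlier allocation at that university exists to learn from. Guessing returns to 50%, and the 10:10 split is kept.

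**The case against.** The strongest reply is that the two assumptions above are not in the protocol. It describes dissemination, then anamnesis and selection, then consent and baseline measures, and only afterwards the assignment of those who agreed. It expects the whole sample within a month. A cohort recruited first and allocated together fits that text, and then nothing could be predicted. This stands, and it is why the point is conditional. The text does not settle the matter the other way either: registration is spread over a month, with weekly audits that order records by date of inclusion.

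Second, duties are divided: the data manager generates the list, a support researcher assigns, and the treating specialist and the data collector are named separately. Nothing says that those who select students see allocations. This also stands. Treatment and selection are both centre-based, so it is plausible, but it is an inference.

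Third, the block size is not published, which is itself some protection. That weakens the certainty figures but not the best-guess figures.

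Fourth, sleep and stress questionnaires come after consent, so at selection staff have only the anamnesis to go on. That limits steering without excluding it.

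Fifth, fixed blocks within centre are a common choice, and the root of the difficulty is the untreated control. With a sham, past allocations would largely be invisible. That is fair, but this protocol describes no sham.

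A reader might infer that everyone can see the arms and that recruiting staff will be able to work out what comes next. The documents do not support that. Knowledge of the arm is unavoidable for participants and treating physiotherapists only. Masking of the evaluator and the analysis is claimed and may be achievable, and the questionnaires are completed online without contact with the researcher.

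**Conclusion.** The concern holds in conditional form. The protocol combines fixed-size blocks, balance within centres of 20 and a control that cannot be masked from participants or therapists, and it leaves out the three facts that would show whether allocation can be predicted: block size, who learns each allocation, and whether randomisation is sequential. If it is sequential and those selecting students see past allocations, 9% to 50% of allocations are certain in advance (given the block size) and 62% to 75% can be guessed correctly. Room for selection bias follows from convenience selection and the anamnesis.

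It would be going too far to conclude that selection bias is present, or that the list is not concealed; the documents show neither. Confidence is medium. The change is still worth making, because it is cheap and because selection bias cannot be reliably repaired after enrolment.

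**What to change.** In RANDOM ASSIGNMENT, replace the fixed-size block sentence with one-step randomisation. For each university, once all consents are signed and all PRE measures are locked, the data manager or support researcher allocates the full list of 20 codes at random, 10 to each arm, in a single operation. State who holds the list, and that no allocation at that university is released before this step.

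The cost is a sentence or two in the protocol, a newly generated list, and a short wait before the first session for students who consent early, within a recruitment period expected to last a month. Balance within each university is kept.

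Randomly varying block sizes should not be adopted as the only change. They would leave about 67% to 70% of guesses correct, and would make guessing easier than now if the intended block is 10 or 20.

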1. SLEEP VARIABLES

1.1 Perceived sleep quality: through a validated sleep quality perception questionnaire, Pittsburgh questionnaire (Escobar Córdoba & Eslava Schmalbach, 2005) (ANNEX 04)

1.2 Salivary cortisol measurement: Through the Soma OFC II cube. The analysis will be performed in real time through the collection of saliva, it is not affected by recent food and drink; Once the swab is in the buffer, your sample is stable for months. It is a validated instrument (Fisher, 2015).

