The correct application of the NXSIGNAL® device, as well as an adequate programming, is of vital importance for the fulfillment of the objective. General guidelines will be established, which must always be followed with the application of NESA microcurrents, and specific guidelines for this particular study, in order to obtain a sample as homogeneous as possible and bring the programming of the device closer to the objective to be pursued. in the clinical trial. General guidelines for the application of NXSIGNAL®.

- The skin must be clean, free of creams and grease, so it will be necessary to clean with alcohol or similar. The device's gloves and socks will be placed in accordance with the established protocols, paying attention to the location of each semi-electrode in its anatomical position. The device has a color system to determine the location of each cable.
- The directing electrode will be located with the skin equally clean, and will be essential for the operation of the technology.
- The use of electronic devices by the patient, less than one meter away, is contraindicated in order to optimize their use. The electrodes are connected to the control console and the targeting electrode located on the intervertebral area between C7 and T1 (cervical area) and will follow the central treatment pattern with the following combination:

Programación X-Signal Estudio Calidad Sueño en Estudiantes

[figure not shown]

Figure 4. The numbers located vertically to the left of the image represent the number of sessions. The central blocks refer to the programs and the application time and in the vertical right column the type of central application of the targeting electrode is defined, located in the cervical area C7.

The default schedule is based on the goals set in this study. The main objective is to improve the quality of sleep. The secondary objectives are to correlate with improving perception of stress and academic performance.

Group 2: Control group without NESASIGNAL[®] application

The same protocol for the analysis of variables is followed, but without performing any type of treatment with the NESASIGNAL device.

DEFINITION OF THE STUDY VARIABLES AND MEASUREMENT INDICATORS:

The variables will be measured before the start of the intervention (PRE), at the end of the intervention (POST) and one month after the end of the study.

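### The protocol and SAP text sets no clock time for salivary cortisol sampling and, at POST, no interval from the last device session, and the between-arm tests do not adjust for timing.

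*Combined protocol and SAP*

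**What the plan says.** The cortisol procedure is in section 1.2, under Sleep Variables. It names the device, says that samples keep for a long time once in buffer, and states: "The analysis will be performed in real time through the collection of saliva, it is not affected by recent food and drink". That is a claim about the assay. It does not say when to sample.

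The section Definition of the Study Variables and Measurement Indicators sets the timing for all outcomes: "The variables will be measured before the start of the intervention (PRE), at the end of the intervention (POST) and one month after the end". Phase 3 of the recruitment section places baseline after consent: "Once the consent is signed, the participant will fill in the participant's demographic characteristics questionnaire (ANNEX 03) and measures of baseline variables". It then says that participants are called to the laboratory "within the corresponding deadlines and indicated in the information sheet of the study". The Design section adds that "both will be evaluated for the same variables at the same times".

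Under Intervention Protocols, treated students attend ten 60-minute sessions, two a week for five weeks, with no session hour given. Controls follow the same measurement protocol "but without performing any type of treatment with the NESASIGNAL device".

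The Statistical Analysis Plan compares groups with an independent-samples t test, or Kruskal-Wallis if the data are not normal. It names no covariates.

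**The concern.** Cortisol depends on time of day. The documents do not mention this; it is general physiology. The plan addresses one feature of sample collection, recent food and drink, and is silent on the hour. A student could be sampled in the morning at PRE and in the afternoon at POST, at any of four universities, without departing from the plan. That variation would go straight into the error term of an unadjusted test.

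The second issue concerns POST only. The plan places POST at the close of the treatment course, which allows a treated student to be sampled straight after session 10. Controls have no sessions and no sham, so they have no matching occasion. If that happened, any short-lived response to an hour of rest or to the device would fall in one arm only and could be read as a lasting benefit. Randomisation would not remove it, because it arises after allocation.

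Cortisol is the only biological measure. The other outcomes are questionnaires and grades.

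**Working it through.** **What each place fixes**

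| Place | Study phase | Clock time | Interval from a session |
|---|---|---|---|
| 1.2 Salivary cortisol | no | no | no |
| Definition of the variables | PRE, POST, one month | no | no |
| Recruitment, Phase 3 | baseline after consent | no (refers to ANNEX 01) | no |
| Design | same times in both arms | no | no |
| Intervention Protocols | session length and frequency | no | no |
| Statistical Analysis Plan | – | no covariate | no covariate |

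The phase is settled. The hour and the distance from a session are not.

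**Inputs for the size of the effect.** The documents give no cortisol mean, SD, effect size or power, and the 80 participants are a pilot number, so there is no stated figure to reproduce. From the documents: 80 participants, two arms balanced within university (40 per arm inferred) and a significance level of 0.05. Assumed: two-sided testing, 80% power, SD = 1 with timing fixed, and everyone analysed. The calculations use the normal approximation.

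Standard error of the difference = √(2/40) = 0.2236 SD.

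Detectable difference = (1.960 + 0.842) × 0.2236 = 0.63 SD.

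**Noise: timing varies alike in both arms.** Let timing add a fraction f to the variance.

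- SE ratio = √(1 + f)
- Detectable difference = 0.6265 × √(1 + f)
- Power at 0.63 SD = Φ(0.63 / (0.2236 × √(1 + f)) − 1.96)
- n per arm for 80% power = 2 × 2.802² × (1 + f) / 0.63², rounded up

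| f (assumed) | SE ratio | Detectable difference (SD) | Power at 0.63 SD | n per arm for 80% |
|---|---|---|---|---|
| 0 | 1.00 | 0.63 | 80% | 40 |
| 0.25 | 1.12 | 0.70 | 71% | 50 |
| 0.50 | 1.22 | 0.77 | 63% | 60 |
| 1.00 | 1.41 | 0.89 | 51% | 80 |

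**Bias: only if timing differs by arm.** Suppose there is no true effect and the arms differ by b SD through timing or closeness to a session.

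Rejection rate = Φ(b/0.2236 − 1.96) + Φ(−b/0.2236 − 1.96).

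| b (assumed, SD) | False-positive rate |
|---|---|
| 0 | 5.0% |
| 0.1 | 7.3% |
| 0.2 | 14.5% |
| 0.3 | 26.9% |
| 0.5 | 60.9% |

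For example, a drift of 0.1 SD per hour and a mean gap of two hours between arms give b = 0.1 × 2 = 0.2. Neither value comes from the documents. The table shows sensitivity and is not an estimate.

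**Which visits are exposed.** PRE comes before the first session. The last visit is a month after the course ends, with no session nearby. Time-of-day noise can affect all three visits; the session question arises only at POST.

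**The case against.** The strongest reply is that the documents do not show bias. Allocation is balanced within each university, so differences between sites in visit hours fall on both arms. The Design section promises evaluation at the same times, and the control-group entry promises the same measurement protocol. No passage says that treated students are sampled around a session, and none describes an acute cortisol response to one. This stands as far as bias is concerned. A reader might infer that the cortisol comparison is confounded by timing, but the text only leaves room for that. The promise of equal times does not close the gap, because in context it refers to the visit schedule.

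A reader might also infer that no sampling rule exists. That goes too far, because ANNEX 01 is cited for deadlines and cannot be seen here. Nor can one conclude that the problem is beyond repair at analysis. Collection time is not listed among the recorded items, but no data-collection form is available, so its absence is not proven. The quality-audit section mentions a time of exposure, which is not described as saliva collection time.

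Two further points stand. The magnitudes are assumptions throughout, and 40 per arm is a best case, since missing one session eliminates a participant. The consequence is also limited: this is a pilot, and the stated objectives name sleep quality, stress perception and academic performance, not cortisol.

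None of this answers the noise argument, which needs no difference between arms.

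**Conclusion.** The point holds in limited form. The protocol and SAP text does not specify the hour of cortisol sampling or, at POST, its interval from the last session, and the planned tests adjust for neither. Following the plan as written leaves time-of-day variation in the error term. If that adds 25% to 100% to the variance, the standard error rises by a factor of 1.12 to 1.41, and power at 0.63 SD falls from 80% to between 71% and 51%. These figures assume 40 analysed per arm and a two-sided 0.05 test.

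Bias at POST is conditional. It needs hours or closeness to a session to differ by arm, which is possible because only one arm has sessions. The false-positive rates above apply only in that case and should not be quoted as the trial's error rate. The daily rhythm itself is taken from general physiology. This is worth correcting because the remedy is cheap, but it does not bear on the questionnaire or grade outcomes.

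**What to change.** Add to section 1.2 and the schedule of measurements:

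- In both arms, take the PRE, POST and one-month saliva samples within one common clock-time window, at the same time for a given student across visits.
- Do not take the POST sample on the day of a device session.
- Record the collection time of every sample.

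In the Statistical Analysis Plan, compare arms on cortisol with ANCOVA, adjusting for PRE cortisol (already collected) and collection time. The sampling rules matter more than the covariate: adjusting for clock time cannot remove an effect of closeness to a session if only one arm is sampled that way. If ANNEX 01 already contains a sampling window, carry it into the protocol text.

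The cost is less flexible appointments for students, at four sites and three visits, and one extra form field. The device sessions do not change.
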